7.7.2 Primary Efficacy Endpoint

 ORR defined above as estimated by the proportion of subjects with a best response of CR or PR during the study.

7.7.3 Secondary Efficacy Endpoint

- OS rate at 6 and 12 months defined as determined by the proportion of subjects who are alive at 6 months and 12 months from the date of first dose of study drug, respectively.
- PFS as determined by the time interval from the date of first dose of study drug to first documented disease progression or death from any cause, whichever occurs first, evaluable.
- DCR as determined by the proportion of subjects with CR, PR, or SD.
- QoL as measured from the date of first dose of study drug/baseline and then every 4 weeks using the EORTC-QLQ-C30 (see Appendix C)

7.7.4 Exploratory Efficacy Variables

- Determine the Efficacy and safety of abemaciclib with regard to the subtypes of biliary tract carcinoma (BTC) including intrahepatic cholangiocarcinoma (IHCC), extra-hepatic cholangiocarcinoma (EHCC), ampullary carcinoma, and gall bladder carcinoma (GBC).
- Analyze the biopsied tumor tissues for molecular profiling (by Caris Life Sciences, Inc®) including genetic mutation in *K-RAS*, *B-RAF*, *TP53*, *INK4A/p16*, *CDKN1A/*p21, *cyclin D*, and *RB* by DNA sequencing (clinical routine).
- Correlate the efficacy of abemaciclib with the mutational status of *K-RAS*, *B-RAF*, *TP53*, *INK4A/p16*, *CDKN1A/p21*, *cyclin D*, and *RB* genes.
- Analyze the collected blood samples for characterization of extracellular vesicles (EVs). Three lavender-top EDTA glass tubes will be used to collect approximately 5 ml of blood in each tube, and one 10-ml green-top sodium heparin tube will be used to collect approximately 7.5 ml of blood in the tube. The collected blood specimens will be processed as described in the Study 18-052 Lab Manual, and the frozen specimens will be stored in freezer boxes and sent to [name] ([contact]), or [name] research staff. The blood specimens will be processed by and stored in [name] laboratory (Captis Diagnostics, Inc., [name]) for characterization of EVs.

8.0 STATISTICAL PLAN

This is a pilot study to confirm tolerability of abemaciclib and provide an estimate of the overall response rate. A sample size of 10 subjects is determined to be minimally sufficient for these pilot study objectives. The primary objective of this study is objective response rate in locally advanced and metastatic biliary tract carcinoma that have failed (tumor progression or patient intolerance) one or more lines of systemic therapies. All participants will be treated with 200 mg twice daily of oral abemaciclib for 28 days being one cycle. Participants will be treated up to 8 cycles or until progression, untoward toxicities or death. Antitumor activities will be evaluated using RECIST v1.1.

8.1 Sample Size and Power Considerations

The primary endpoints is overall response rate (ORR). A sample size of 10 subjects is determined to be minimally sufficient for these pilot study objectives.

8.2 Analysis Sets/Populations

8.2.1 Enrolled Participants

The set of enrolled participants includes all participants who provide informed consent to participate in the study and who meet all inclusion and exclusion criteria, regardless of whether or not a participant took any study drug.

8.2.2. Safety Analysis Set

The safety analysis set for this study will include participants who receive 1 or more doses of study drug.

8.2.3 Data Handling Conventions

For all variables, only the observed data from the participants will be used in the statistical analyses. There is no plan to estimate missing data. Treated participants without response assessment after dosing will be considered as non-responders.

8.3 Study Population

The set of enrolled participants will be used for all study population summaries unless otherwise noted.

8.3.1 Participant Disposition

Data from participants who are screened, participants screened but not enrolled, reason for non-enrollment, participants enrolled, participants enrolled but not treated, participants in the safety sets, participants who complete the study, and participants who withdraw from the study will be summarized using descriptive statistics. Data from participants who withdraw from the study will also be summarized by reason for withdrawal using descriptive statistics.

8.3.2 Demographic and Baseline Characteristics

Participant demographic and baseline characteristics, including age, sex, race, medical history, disease types, biomarkers, prior medications, and ECG and physical examination findings, will be summarized using descriptive statistics. For continuous variables, descriptive statistics (number [n], mean, standard deviation, standard error, median, minimum, and maximum) will be provided. For categorical variables, participant counts and percentages will be provided. Categories for missing data will be presented if necessary.

8.4 Efficacy Analysis

8.4.1 Primary Efficacy Endpoint

The primary efficacy endpoint is ORR evaluated using RECIST v1.1. A responder is defined as a participant with a best response of CR and PR during study. Confirmation of CR and PR as assessed by RECIST v1.1 is needed no sooner than 4 weeks after the initial observation of response.

8.4.2 Secondary Endpoints

The secondary efficacy endpoints are as follows:

- OS rate at 6 and 12 months defined as determined by the proportion of subjects who are alive at 6 months and 12 months from the date of first dose of study drug, respectively.
- PFS as determined by the time interval from date of first dose of study drug to first documented disease progression or death from any cause, whichever occurs first.
- DCR as determined by the proportion of subjects with CR, PR, or SD.
- QoL as measured from the date of first dose of study drug/baseline and then every 4 weeks using the EORTC-QLQ-C30 (see Appendix C). The EORTC QLQ-C30 is a copyrighted instrument, which has been translated and validated in over 100 languages and is used in more than 3,000 studies worldwide. Presently QLQ-C30 Version 3.0 is the most recent version. It is supplemented by disease-specific modules for e.g. Breast, Lung, Head & Neck, Esophageal, Ovarian, Gastric, Cervical cancer, Multiple Myeloma, Esophago-Gastric, Prostate, Colorectal Liver Metastases, Colorectal and Brain cancer which are distributed by the EORTC Quality of Life Department. Other disease specific modules are under development but not yet validated.

8.4.3 Planned Method of Analysis

The primary and secondary efficacy endpoints, which include PFS, DCR, OS and QoL will be tabulated and graphed as appropriate. The Kaplan-Meier survival curve will be graphed with confidence intervals. A 5% level test of the median survival, based on an exponential maximum likelihood estimator test, will be conducted to determine if median survival is statistically greater than 2.8 months. Adverse events and serious adverse events will be annotated and tabulated to allow for a quantitative assessment of the safety and tolerability of abemaciclib. Potential factors associated with the efficacy of abemaciclib, including subtypes of BTC subtypes, and tumor molecular profiles, will be explored with a Cox proportional hazards model. Reproducible statistical reports will be produced.

The QLQ-C30 is composed of both multi-item scales and single-item measures including a global health status/QoL scale, five functional scales and three multi-item symptom scales and six single item scales. For the multi-item scales, the raw score, RS, is calculated by taking the mean of the individual item scores. Then a linear transformation is applied to standardize the raw score so that scores range from 0 to 100. The linear transformations for each scale type (functional/symptom/global health status) are different and clearly documented in the EORTC QLQ-C30 Scoring Manual. Descriptive statistics of the QLQ-C30 scales will be reported and Spaghetti plot graphics will be produced to visualize the responses. No statistical analyses are planned for this secondary measure.

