1.2.2 Secondary Objectives

- To determine PFS
- To determine the DCR
- To determine the OS rate at 6 and 12 months
- To determine QoL using EORTC-QLQ-C30 (see Appendix C)

1.2.3 Exploratory Objectives:

- Determine the efficacy and safety of abemaciclib with regard to the subtypes of BTC including IHCC, EHCC, ampullary carcinoma, and GBC.
- Analyze the biopsied tumor tissues for molecular profiling including genetic mutation in *K-RAS*, *B-RAF*, *TP53*, *INK4A*/*p16*, *CDKN1A*/*p21*, *cyclin D* and *RB* by DNA sequencing (clinical routine).
- Correlate the efficacy of abemaciclib with the mutational status of *K-RAS*, *B-RAF*, *TP53*, *INK4A/p16*, *CDKN1A/p21*, *cyclin D*, and *RB*.
- Analyze the collected blood samples for characterization of EVs including genetic mutations and metabolic profiles.

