Approximately 10,000 new cases of BTC are reported each year within the United States (Siegel et al, 2017). For patients with BTC, the majority (80-90%) is diagnosed with locally advanced or metastatic disease, for which surgical resection with curative intent is not feasible (Marks and Yee, 2015a). Palliative systemic chemotherapy with or without radiation therapy remains the only treatment option (Wyluda and Yee, 2015). However, the literature regarding treatment results is limited because most studies are small, reports consist of treatment of bile duct carcinoma, gallbladder carcinoma, ampullary carcinoma, and pancreatic or hepatocellular carcinoma due to paucity of patients. Despite being in a similar anatomic location, the biological behavior may vary. In general, though, no single drug or combination has consistently increased survival beyond the expected 6-8 months.

The current standard first-line chemotherapy using gemcitabine and cisplatin produces limited survival benefits, with an overall survival of 12.7 months and progression-free survival of 8 months, as compared to gemcitabine, 8.1 months and 5 months, respectively (Valle et al, 2010). Typically, the disease will progress, and currently there is no standard second-line treatment. Despite treatment, the clinical outcomes of patients with BTC are generally poor, with a 2-year survival rate of 13% for patients with gallbladder carcinoma and less than 5% for cholangiocarcinoma (Marks and Yee, 2015b).

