Clinical studies have been attempted to improve treatment response in patients with BTC by using various combinations of chemotherapeutic drugs and targeted agents, though with limited success (Wyluda and Yee, 2015; Marks and Yee, 2015a; Marks and Yee, 2015b). While epidermal growth factor receptors (ERBB-1, ERBB-2) are aberrantly over-expressed or amplified in BTC, the combination of either erlotinib or cetuximab with cytotoxic drugs have not produced significant clinical benefits (Lee et al, 2012; Malka et al, 2014). Conceivably, resistance of biliary tract tumors may be related to underlying genetic mutations, particularly *K-RAS*, *B-RAF*, *TP53*, *INK4A/p16*, and *RB*. Tumors with these mutations are typically aggressive and resistant to chemotherapy-induced apoptosis. Currently, there are no actionable agents that effectively target mutated K-RAS, p53, INK4A/p16, or RB. Targeting the oncogenes and tumor suppressor genes that control tumor growth may provide new opportunities to improve treatment responses for patients with BTC. Mutations in *K-RAS*, *B-RAF*, *TP53*, and *INK4A/p16* have been demonstrated in BTC (Chang et al, 2014; Hanada et al, 1999; Rashid et al, 2002; Robertson et al, 2013; Saetta et al, 2004; Suto et al, 2000; Tannapfel et al, 2000; Tannapfel et al, 2006; Marks and Yee, 2015a), and they may play important roles in development and progression of BTC.

The incidence of oncogenic mutations in *K-RAS* has been reported to be 17% to 59% of gallbladder carcinoma (GBC), 23% to 100% of extra-hepatic cholangiocarcinoma (EHCC), and 0% to 56% in intra-hepatic cholangiocarcinoma (IHCC). At a relatively low frequency, mutations in *B-RAF* were found in 1% of GBC, 3% of EHCC, and 5% of IHCC. Similarly, mutations in *PI3KCA* are present in 14% of GBC, 7% of EHCC, and 5% of IHCC. The reported incidence of mutations in *TP53* is 31% to 92% in GBC, 33% to 73% in EHCC, and 11% to 37% in IHCC. In BTC, inactivation of INK4A/p16 has been shown to occur through distinct mechanisms including deletion or point mutation of the *INK4A/p16* gene, and hypermethylation of the 5' regulatory regions of *INK4A/p16*.

In particular, 60-80% of BTC exhibit point mutations in the *INK4A/p16* gene. These data suggest that the mutated K-RAS, p53, and INK4A/p16 are potential therapeutic targets in BTC.

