Abemaciclib is also being studied in the treatment of other types of cancer. In a multicenter study that involved phase I dose escalation followed by tumor-specific cohorts, anti-tumor activity of abemaciclib was observed in patients with advanced solid tumors. These include breast cancer, nonsmall cell lung cancer, colorectal carcinoma, melanoma, ovarian cancer, endometrial cancer, and glioblastoma. Importantly, this study demonstrates a better disease control rate in patients with lung adenocarcinoma carrying K-RAS mutation than in those with wild-type K-RAS treated with abemaciclib (Patnaik et al, 2016). Similarly, patients who responded to abemaciclib include one with metastatic melanoma harboring both N-RAS mutation and loss of INK4A/p16 gene. In this clinical study, the dose-limiting toxicity was grade 3 fatigue. Other common treatment-related AEs occurred in the gastrointestinal, renal, or hematopoietic systems. An acceptable safety profile and antitumor activity of abemaciclib were also demonstrated in another clinical study (Fujiwara et al, 2016). This is a phase I study using dose escalation of abemaciclib as a single agent for Japanese patients with advanced cancer. In this study of 12 patients, tumor response was demonstrated in two patients, one with breast cancer and one with neuroendocrine carcinoma. Taken together, abemaciclib produces anti-tumor effect as a single agent in various malignancies, and it possibly overcomes therapeutic resistance due to mutations in K-RAS and INK4A/p16.

It is known that BTC carry mutations in oncogenes and tumor suppressor genes that directly or indirectly regulate CDK4 and CDK6, but the efficacy of abemaciclib has not been investigated in BTC. Clinical study (as in this proposal) is indicated to test the hypothesis that abemaciclib prolongs

PFS in patients with advanced BTC by improving anti-tumor response. Exploring the potential therapeutic use of abemaciclib and correlation of its efficacy with tumor molecular profiles in advanced BTC is expected to create new treatment options, and generate insight into the roles of CDK4/6 in the pathogenesis of BTC. Furthermore, this study will help pave the way to future investigation of combination therapy using abemaciclib for improving treatment response and survival in patients with BTC.

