7.1 General Design/Phase/Schema

This is an open label pilot study to determine the efficacy and safety/tolerability of abemaciclib in participants with locally advanced, unresectable, or metastatic biliary tract cancer who have failed one or more lines of systemic therapy, or treatment-naïve subjects who either decline or being considered not a good candidate first-line systemic chemotherapy per the opinion of the treating physician 7.1.1 Enrollment/Randomization

This is a non-randomized study and thus participants will be enrolled sequentially. Participants will be screened for eligibility after signing the informed consent form.

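### With one arm, the exploratory Cox model can show whether outcome differs by subtype or mutation, but not whether abemaciclib's efficacy does

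*Combined protocol and SAP*

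**What the plan says.** Section 8.4.3 plans a Cox regression: "Potential factors associated with the efficacy of abemaciclib, including subtypes of BTC subtypes, and tumor molecular profiles, will be explored with a Cox proportional hazards". It does not name the outcome (PFS or OS), the covariate set, a null hypothesis or a significance level for that model. The only 5% test in the section concerns median survival.

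The analysis serves two exploratory objectives in 1.2.3, repeated in 7.7.4: "Determine the efficacy and safety of abemaciclib with regard to the subtypes of BTC including IHCC, EHCC, ampullary carcinoma, and GBC", and "Correlate the efficacy of abemaciclib with the mutational status of" seven named genes.

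On design, 7.1.1 states: "This is a non-randomized study and thus participants will be enrolled sequentially". Section 8.0 adds: "All participants will be treated with 200 mg twice daily of oral abemaciclib for 28 days being one cycle". There is no comparator or external control, and no text separates prognosis from drug effect.

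On how efficacy is judged, 7.7 says it is assessed by tumor response, and 8.4.1 requires CR and PR to be confirmed.

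**The concern.** The objectives ask whether abemaciclib works differently across subtypes and mutations. The Cox model asks whether time to an event differs across those groups when everyone is treated. The two questions coincide only if the marker has no bearing on outcome apart from the drug.

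The background gives reason to doubt that. Section 2.2 says of K-RAS, B-RAF, TP53, INK4A/p16 and RB: "Tumors with these mutations are typically aggressive and resistant to chemotherapy-induced apoptosis". Of the different sites it says: "Despite being in a similar anatomic location, the biological behavior may vary". It then hypothesises that CDK inhibition helps mutated tumors in particular. If both statements are right, prognosis and drug effect pull the hazard ratio in opposite directions.

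Two errors are possible. A hazard ratio above 1 for a mutation could be reported as lower efficacy when it reflects prognosis, or a benefit confined to mutated tumors could appear as no association. The risk of misreading is foreseeable: the clinical part of 2.4 already takes a difference in disease control by K-RAS status, among lung cancer patients who all received abemaciclib, as support for a drug-marker effect.

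**Working it through.** The plan gives no effect size, event count or power for the Cox model, so there is no figure of its own to reproduce.

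**1. What the hazard ratio estimates.** Let P be the marker's prognostic HR without abemaciclib, and D+ and D− the drug's HR in marker-positive and marker-negative patients. With everyone treated:

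Cox HR = (P × D+) / D− = P × (D+/D−)

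The objective concerns D+/D−. Treatment does not vary, so no drug-by-marker term can be fitted and only the product is estimable.

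**2. Numerical check.** Exponential times, half marker-positive, n = 20,000; P and D are assumptions.

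| P | D− | D+ | Formula | Simulated Cox HR |
|---|---|---|---|---|
| 2 | 1 | 1 | 2 | 2.00 |
| 2 | 0.5 | 0.5 | 2 | 2.05 |
| 2 | 1 | 0.5 | 1 | 1.00 |
| 1 | 1 | 0.5 | 0.5 | 0.50 |

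Rows 1 and 2 show prognosis alone producing an HR of about 2. Row 3 shows a halving of hazard in marker-positive patients disappearing.

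**3. What the documents imply for subtype.** Section 2.2 gives 2-year survival of 13% for gallbladder carcinoma and under 5% for cholangiocarcinoma. The protocol says abemaciclib has not been investigated in BTC, so this difference is not a drug effect. Under proportional hazards:

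HR (cholangiocarcinoma vs gallbladder) ≥ ln(0.05)/ln(0.13) = 2.996/2.040 = 1.47

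A drug-effect ratio of 1/1.47 = 0.68 in favor of cholangiocarcinoma would cancel it. No comparable figure is given for any mutation.

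**4. Illustrative rejection rates.** Assume one marker, half positive, no censoring, a two-sided 5% likelihood-ratio test (not in the plan) and the same drug effect in both groups.

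| Assumed P | n = 10 | n = 20 |
|---|---|---|
| 1 | 6.5% | 6% |
| 1.5 | 10% | 14% |
| 2 | 17% | 30% |

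For masking, take a true D+/D− of 0.33. Power is 31% (n = 10) and 60% (n = 20) when P = 1, and falls to 10% and 14% when P = 2.

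**5. Scale of the intended question.** Assume a hypothetical 1:1 randomized comparator, 50% marker prevalence, two-sided 5% and 80% power:

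events = 16 × (1.960 + 0.842)² / ln(ratio)²

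This gives 262 events for a ratio of HRs of 2, and 105 for a ratio of 3. The trial has 10 evaluable and up to about 20 enrolled participants, and no comparator.

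**The case against.** **The plan explores; it does not test.** This stands. Section 8.4.3 sets no null hypothesis or alpha for the Cox model. A reader might infer from step 4 that the plan has a known false-positive rate. It does not: those rates depend on a test the plan does not contain and on assumed prognostic HRs.

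**The protocol does not establish that the mutations are prognostic.** This largely stands. Section 2.1 says their part in chemoresistance and progression is unclear, and the sentence quoted from 2.2 follows one that is openly conjectural. It does not cover CDKN1A/p21 or cyclin D. The one quantitative contrast concerns subtype and gives a lower bound of about 1.47, not 2 or 3. A 50% marker split also cannot describe B-RAF, reported in 1% to 5% of cases. The documents suggest that the markers may matter apart from the drug; they do not prove it.

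**The protocol does not rest new treatments on the marker analysis alone.** A reader might infer that from the statement in 2.4 that "correlation of its efficacy with tumor molecular profiles in advanced BTC is expected to create new treatment options". The full subject of that sentence also includes exploring the drug's therapeutic use, so the stronger reading is not supported.

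**Substitute analyses may carry the same defect.** This stands for two candidates.
- Best percent change in tumor size also reflects growth rate. In a simulation with no drug effect, median 8-week growth of about 12% and growth doubled in mutated tumors (all assumed), a rank test rejected in 18% at n = 10 and 46% at n = 20.
- The ratio of PFS on abemaciclib to time to progression on the prior line is biased if mutated tumors are chemoresistant. With independent exponential times and equal hazards on both lines, a ratio of at least 1.3 has probability 1/(1 + 1.3) = 43%. Doubling the prior-line hazard, with abemaciclib PFS unchanged, gives 2/(2 + 1.3) = 61%. The ratio is also unavailable for treatment-naive participants and may be for those who stopped a prior line through intolerance.

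**Any single-arm pilot has this limit.** True, and no method here removes it. That supports correcting the label rather than leaving it unqualified.

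**Conclusion.** The point holds as one of interpretation. In this design the planned model estimates differences in outcome among treated participants, whereas 8.4.3 presents the result as factors in abemaciclib's efficacy. This follows from the single arm and needs no assumption about size. Whether it misleads in practice depends on how prognostic the markers are. For subtype the documents imply an HR of at least about 1.47, assuming proportional hazards; for the mutations they give no figure.

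Severity is low. The analysis is labelled exploratory, estimates from 10 to 20 participants will be very imprecise in any case (a separate limitation), and the primary ORR estimate is unaffected. The documents do not support inferring that the trial's main conclusion is compromised, or that a false marker finding is likely at a stated rate.

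**What to change.** In 8.4.3, name the Cox outcome (PFS or OS) and replace the sentence on factors with wording such as:

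*Cox model results for BTC subtype and molecular profile are descriptive associations with outcome among treated participants. They will not be interpreted as differences in the efficacy of abemaciclib.*

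For the efficacy-by-marker objectives in 1.2.3 and 7.7.4, list or tabulate confirmed CR/PR, the protocol's own efficacy measure (7.7, 8.4.1), by subtype and mutation status, with no test. Keep this descriptive too: 8.2.3 counts treated participants without a post-dose assessment as non-responders, so early deterioration can still affect it. Do not add the PFS ratio to the prior line. If best percent change is shown, do not present it as free of prognosis.

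The cost is a change of wording and one table or listing from RECIST assessments already required, with no added participants or visits. The downside is a more modest exploratory conclusion resting on few responders.
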